10.2 Analysis of Adverse Events

A treatment-emergent Adverse Event (TEAE) is defined as an adverse event with an onset date that is on or after the first dose of open-label study drug, and no more than 30 days after the last dose of open-label study drug; or an adverse event with onset date before the first dose of open-label study drug, but increased in severity on or after the first dose of

open-label study drug, and no more than 30 days after the last dose of open-label study drug.

Events where the onset date is the same as the study drug start date are assumed to be treatment-emergent. If an incomplete onset date was collected for an adverse event, the event will be assumed to be treatment-emergent unless there is other evidence that confirms that the event was not treatment-emergent (e.g., the event end date was prior to the open-label study drug start date).

Adverse event data will be presented by system organ classes (SOCs) and preferred terms (PTs) using the Medical Dictionary for Drug Regulatory Activities (MedDRA) version 19.0 or most up to date version. All adverse event tables will be sorted in alphabetical order by SOC and PT and descending percentages in the Any upadacitinib group.

10.2.1 Overview of Adverse Events Rates per 100 Patient-Years of Study Drug Exposure

The number and percentage of subjects experiencing TEAEs will be summarized for each exposure group in the open-label treated population for the following AE categories:

- All TEAEs
- Treatment-emergent serious adverse events (SAEs)
- Treatment-emergent severe adverse events
- TEAEs reasonably possibly related to study drug
- TEAEs of special interest
- TEAEs leading to discontinuation of study drug
- TEAE leading to death
- All death

For this calculation, 1 year will be considered to be 365.25 days. For each exposure group, the numerator of the overall rate will be the total number of TEAEs reported for

the event; that is, a subject can contribute more than one event to the numerator. For each treatment group, the denominator of the rates will be the total number of days exposed to study drug summed across all treated subjects divided by 365.25. Please refer to Section 8.1 for the calculation of study drug exposure. The AE rate per 100 patient-years of exposure will be calculated as $(\text{[numerator/denominator]}) * 100$. The number of AEs reported (numerator), the total number of years of study drug exposure (denominator), and the AE rate per 100 patient-years will be presented for each exposure group.

In the AE overview summary, any event with an unknown severity will be considered as severe and any AE with an unknown relationship will be considered as having "reasonable possibility" of being related to study drug.

Additional AEs may be considered for tabulation/summary based on recommendations from Clinical and Safety as deemed appropriate.

10.2.2 Adverse Events Rates per 100 Patient-Years of Study Drug Exposure by System Organ Class and Preferred Term

the TEAE rate per 100 patient-years of exposure will be tabulated by SOC and MedDRA PT for each exposure group in the open-label treated population. The SOCs will be presented in alphabetical order, and the PTs will be presented in alphabetical order within each SOC.

The following summaries of adverse events will be generated:

- All TEAEs
- Treatment-emergent serious adverse events (SAEs)
- Treatment-emergent severe adverse events
- TEAEs reasonably possibly related to study drug
- Frequent TEAEs (reported at ≥ 2 E/100PY in any exposure group)
- TEAEs leading to discontinuation of study drug
- TEAE leading to death

10.2.3 Serious Adverse Events (Including Deaths) and Adverse Events Leading to Study Drug Discontinuation Rates per 100 Patient-Years of Study Drug Exposure

All serious adverse events (SAEs), deaths, and adverse events leading to discontinuation of study drug will be summarized by SOC and PT or each exposure group.

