## **6.3 Definitions**

### **6.3.1 Adverse Event**

An adverse event (AE) is defined as any untoward medical occurrence in a patient or clinical investigation subject administered a pharmaceutical product and which does not necessarily have a causal relationship with this treatment. An adverse event can therefore be any unfavorable and unintended sign (including an abnormal laboratory finding), symptom, or disease temporally associated with the use of a medicinal (investigational) product, whether or not the event is considered causally related to the use of the product.

Such an event can result from use of the drug as stipulated in the protocol or labeling, as well as from accidental or intentional overdose, drug abuse, or drug withdrawal. Any worsening of a pre-existing condition or illness is considered an adverse event.

Worsening in severity of a reported adverse event should be reported as a new adverse event. Laboratory abnormalities and changes in vital signs are considered to be adverse events only if they result in discontinuation from the study, necessitate therapeutic medical intervention, (meets protocol specific criteria [see Section 6.10 regarding toxicity management]) and/or if the investigator considers them to be adverse events.

An elective surgery/procedure scheduled to occur during a study will not be considered an adverse event if the surgery/procedure is being performed for a pre-existing condition and

the surgery/procedure has been pre-planned prior to study entry. However, if the pre-existing condition deteriorates unexpectedly during the study (e.g., surgery performed earlier than planned), then the deterioration of the condition for which the elective surgery/procedure is being done will be considered an adverse event.

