### **8.1.6.2 Analysis of Adverse Events**

#### **8.1.6.2.1 Treatment-Emergent Adverse Events**

Adverse events (AEs) will be coded using the Medical Dictionary for Regulatory Activities (MedDRA) dictionary. Treatment-emergent adverse events, defined as AEs that began or worsened in severity after initiation of open-label study drug upadacitinib in

this OLE study, will be tabulated by system organ class (SOC) and MedDRA preferred term.

Adverse events starting more than 30 days following discontinuation of study drug will not be included in summaries of treatment-emergent AEs. Adverse events starting more than 30 days following discontinuation of study drug will be summarized separately as post-treatment AEs.

When summarizing adverse events by relationship or severity, if a subject has an event with unknown severity or relationship then the subject will be counted in the severity/relationship categories of "unknown" even if the subject has a second occurrence of the same event with a severity/relationship present. The only exception is if the subject has a second occurrence of the same event with the most extreme severity (i.e., "severe") or a relationship category of "reasonable possibility." In this case, the subject will be counted under these most extreme severity/relationship categories.

The AEs of special interest (including but not limited to serious infection, opportunistic infection, herpes zoster, TB, gastrointestinal perforations, malignancies, MACE, renal dysfunction, anemia, increased CPK, drug-related hepatic disorders and thrombotic and embolic events) will be summarized.

Subjects reporting more than 1 AE for a given MedDRA preferred term will be counted only once for that term using the most severe incident in each study period. Subjects reporting more than 1 type of event within an SOC will be counted only once for that SOC.

Frequencies and percentages of subjects with treatment-emergent AEs will be summarized as follows:

- Any event
- By system organ class, and preferred term
- By system organ class, preferred term and maximum relationship

- By system organ class, preferred term and maximum severity
- Any event and by system organ class and preferred term for events resulting in death
- Any event and by system organ class and preferred term for events resulting in study drug discontinuation
- Any event and by system organ class and preferred term for serious events

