10.2.4 Frequent Adverse Events by System Organ Class and Preferred Term

TEAEs occurring at ≥ 2 E/100PY in any of the exposure groups will be summarized by MedDRA PT in decreasing rate.

10.2.5 Adverse Events of Special Interests Rates per 100 Patient-Years of Study Drug Exposure

The Adverse Events of Special Interests (AESI) categories will be summarized and presented for each exposure group using SOC and MedDRA PT. The AESI categories will be identified per Standard MedDRA Queries (SMQs)/Company MedDRA Queries (CMQs) in [Table 5](#) below. Adjudicated cardiovascular events will be summarized and presented by treatment groups using CAC adjudicated categories.

Table 5. AESI for Upadacitinib with SMQs/CMQs/PTs Searches

AESI	Type of MedDRA Query	Broad or Narrow Search	SMQ/CMQ Search Criteria
Serious Infections	CMQ		"Infections" – Subset for SAEs
Opportunistic Infection excluding Tuberculosis and Herpes Zoster	CMQ		"Opportunistic Infection excluding Tuberculosis and Herpes Zoster"
Possible Malignancy	SMQ	Narrow	"Malignancies"
Malignancy	SMQ		"Malignant tumours"
Non-Melanoma Skin Cancer (NMSC)	SMQ	Narrow	Skin Malignant tumours (Narrow SMQ) removing Melanoma CMQ
Malignancy excluding NMSC			"Malignant tumours" SMQ removing NMSC output
Lymphoma	SMQ		"Malignant Lymphomas"
Hepatic Disorder	SMQ	Narrow	"Drug Related Hepatic Disorders"
Adjudicated Gastrointestinal Perforations	Output from adjudication		
Anemia	CMQ		"Non-Hemolytic and Non-Aplastic Anemias"
Neutropenia	CMQ		"Hematological Toxicity – Neutropenia"
Lymphopenia	CMQ		"Hematological Toxicity – Lymphopenia"
Herpes Zoster	CMQ		"Herpes Zoster"
Creatine Phosphokinase (CPK) Elevation	PT		Search only for the PT of "Blood creatine phosphokinase increased"
Renal Dysfunction	SMQ	Narrow	"Acute Renal, Failure"
Active Tuberculosis	CMQ		"Active Tuberculosis"
Adjudicated Cardiovascular Events	Output from CAC		
MACE*			
Cardiovascular Death			
Non-fatal Myocardial Infarction			
Non-fatal Stroke			

Table 5. AESI for Upadacitinib with SMQs/CMQs/PTs Searches (Continued)

AESI	Type of MedDRA Query	Broad or Narrow Search	SMQ/CMQ Search Criteria
Undetermined/Unknown Cause of Deaths			
Other Cardiovascular events			
Adjudicated Thrombotic Events	Output From CAC		
Venous Thromboembolic Events**			
Deep Vein Thrombosis			
Pulmonary Embolism			
Other Venous Thrombosis			
Arterial Thromboembolic Events (non-cardiac, non-neurologic)			

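### SAP adverse-event tables by SOC/PT and by AESI give only events per 100 patient-years, without the once-per-subject counts that the protocol plans and without confidence intervals

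*SAP*

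**What the plan says.** **The rate.** SAP 10.2.1 sets the numerator: "the numerator of the overall rate will be the total number of TEAEs reported for" the event concerned, with the clarification that "that is, a subject can contribute more than one event to the numerator". For the denominator, "the denominator of the rates will be the total number of days exposed to study drug summed across all treated subjects divided by 365.25". The output is the event count, the patient-years, "and the AE rate per 100 patient-years will be presented for each exposure group". No interval is listed.

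**The tables that use it.** SAP 10.2.2 states that "the TEAE rate per 100 patient-years of exposure will be tabulated by SOC and MedDRA PT for each exposure group". SAP 10.2.4 defines frequent events as those at 2 or more events per 100 PY in any exposure group. SAP 10.2.5 is headed as rates per 100 PY and says: "The Adverse Events of Special Interests (AESI) categories will be summarized and presented for each exposure group using SOC and MedDRA PT". It gives no other numerator. SAP Section 10 mentions no confidence interval. SAP 9.2 gives 95% intervals for the efficacy endpoints.

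**Subject counts.** SAP 10.2.1 specifies numbers and percentages of subjects for eight overview categories, one of which is all AESIs together. Protocol 8.1.6.2.1 goes further. It plans frequencies and percentages of subjects by SOC/PT and for AESIs, under the rule: "Subjects reporting more than 1 AE for a given MedDRA preferred term will be counted only once for that term". The same rule applies within an SOC.

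**Recording.** Protocol 6.3.1: "Worsening in severity of a reported adverse event should be reported as a new adverse event". Protocol 6.5 grades severity on the Rheumatology Common Toxicity Criteria, which have four grades (Appendix M).

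**The concern.** Three features combine. The SAP counts records. The protocol's recording rule can turn one continuous episode into several records. No SAP rule joins those records again. Below the overview, no subject count is specified that would let a reader see this in the tables.

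Protocol 5.6 describes collecting long-term safety and tolerability data as the primary objective, so these tables are the study's central output. For a single AESI, a tabulated count of two could be two subjects or one subject with two records. Some exposure groups may also be small, notably the one after down-titration, and a rate there without an interval gives no direct sign of how little it is based on.

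**Working it through.** The documents give no expected AE rate, event count or exposure per group, so there is no planned figure to reproduce. The check covers whether multiple scoring can occur, what it could do, and how imprecise small-group rates are.

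**1. Can one episode score more than once?** Under Protocol 6.3.1 a worsening creates a new AE. SAP 10.2 treats an AE with onset on or after the first open-label dose, and up to 30 days after the last, as treatment-emergent, so the new record qualifies. SAP 10.2.1 then counts every record. An episode that moves stepwise from Grade 1 to Grade 4 can give up to four.

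**2. Where does it matter?**
- *Exposed:* the all-TEAE tables by SOC/PT, the cut-off for frequent events, and AESIs found by MedDRA query (for example herpes zoster, hepatic events, cytopenias, CPK).
- *Largely not exposed:* MACE, VTE and gastrointestinal perforation, which SAP Table 5 takes from adjudication.
- *Less exposed:* SAE, severe-AE and serious-infection tables, which take only qualifying records, so earlier mild or non-serious records of the same episode drop out.

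**3. Upper bound on exposure.** 494 subjects × 312 weeks × 7 / 365.25 = 2,954 PY if everyone completes. The cut-off of 2 per 100 PY is then 0.02 × 2,954 = about 59 records. At the other end, one record meets it in any group with 50 PY or less (1/50 × 100 = 2.0).

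**4. Illustration of multiple scoring.** Assumed: 2,000 PY, and 30 subjects with one episode each of a given PT. The denominator is held at 2,000 PY for simplicity.

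| Worsening | Records | Events per 100 PY |
|---|---|---|
| none | 30 | 30/2,000 × 100 = 1.50 |
| 10 episodes, once | 40 | 2.00 |
| 10 episodes, twice | 50 | 2.50 |
| 10 episodes, three times | 60 | 3.00 |

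The number of affected subjects is 30 in every row. In the second row the PT becomes frequent with nobody else affected.

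**5. Which interval?** Exact Poisson limits are chi-square quantiles: lower = χ²(0.025; 2k)/2 and upper = χ²(0.975; 2k+2)/2, each divided by PY and multiplied by 100. For 30 first events in 2,000 PY they are 1.01 to 2.14. For the 40 records the same formula gives 1.43 to 2.72, but it treats records of one subject as independent. With the variance taken as the sum of squared records per subject, 20 × 1² + 10 × 2² = 60, the standard error is √(60/40) = 1.22 times larger and the interval is 1.24 to 2.76. With three worsenings the factor is √(180/60) = 1.73. A first-event count avoids the problem, because each subject contributes at most one event.

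**6. Precision at small exposure** (assumed PY, exact 95% limits).

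| Events | PY | Rate per 100 PY | 95% limits |
|---|---|---|---|
| 0 | 100 | 0 | up to 3.69 |
| 1 | 50 | 2.0 | 0.05 to 11.14 |
| 2 | 100 | 2.0 | 0.24 to 7.22 |
| 10 | 1,500 | 0.67 | 0.32 to 1.23 |

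**The case against.** **The two counting rules are different statistics.** The protocol's once-per-term rule governs subject frequencies. The SAP's rate is an event rate and says so openly. This stands. Events per 100 PY is a legitimate summary, and a reader who inferred that it is wrong, or that it contradicts the protocol, would go too far. What remains is an omission: the subject counts are not carried into SAP 10.2.2, 10.2.3 or 10.2.5. SAP 10.2 does sort AE tables by descending percentages, which suggests that subject percentages may be expected, but none is specified below the overview.

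**Other outputs partly fill the gap.** SAP 10.1 plans a listing of subjects with TEAEs by SOC and PT. SAP 10.2.6 lists SAEs, deaths and AEs leading to discontinuation. SAP 10.3 has subject-level laboratory tables, including liver thresholds. Affected subjects can therefore largely be recovered by hand. That narrows the gap, but a listing does not replace a specified statistic.

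**The most serious AESIs are poor examples of double scoring.** This also stands. MACE and VTE are adjudicated. Protocol 5.4.1 withdraws subjects with confirmed deep vein thrombosis or pulmonary embolism and, with stated exceptions, malignancy, so repeat on-drug records are limited. A reader might infer that these rates are inflated by severity records, and the documents do not support that.

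**An interval cannot settle a dose question.** Correct. The exposure groups in SAP 8.1 arise from titration driven by response and tolerability, not from randomisation, and the SAP plans no tests. An interval would show precision only. Event counts and patient-years are printed beside the overview rates, so a simple interval could be computed there, though a Poisson interval on repeated records would be too narrow.

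**Conclusion.** The point holds as a SHOULD-FIX. For SOC/PT and individual AESIs the SAP specifies only a record-based event rate. The once-per-subject numbers and percentages of Protocol 8.1.6.2.1 are specified only for pooled overview categories, and no AE rate has a stated precision. Severity worsening can make one episode score more than once, mainly in the all-TEAE tables, the cut-off for frequent events and query-based AESIs.

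The size is unknown. Neither document gives the frequency of worsening or the exposure per group. The move from 1.50 to 2.00 per 100 PY rests on the assumed 2,000 PY, 30 subjects and ten worsening episodes. A reader might infer a general inflation of 10 to 20% by supposing that this share of episodes worsens once, but that only restates the supposition. That the 2 per 100 PY cut-off can be met by a single record in a group of 50 PY or less is plain arithmetic. Whether any group is that small is not known from the documents.

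**What to change.** Keep events per 100 PY. In SAP 10.2.2, 10.2.3 and 10.2.5, add for each exposure group:

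1. n (%) of subjects with at least one event, once per PT and once per SOC, as Protocol 8.1.6.2.1 plans, and for each AESI separately.
2. For SAEs and each AESI, subjects with a first event per 100 PY, with exposure censored at the first event in that exposure group, and an exact Poisson 95% interval. State that a subject who changes dose is at risk afresh in the next group, so the handling of switching is explicit.
3. A footnote that events per 100 PY counts severity-worsening records separately. Merge such records only if those of one episode can be linked by PT and contiguous dates; the documents show no CRF field that links them.
4. A sentence that the intervals describe precision and do not support dose comparisons, because the groups arise from titration.

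Cost: SAP wording, some extra programming and slightly longer tables. Items 1 and 2 use AE dates and exposure that are already collected.

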8.0 Study Drug Exposure and Compliance

8.1 Study Drug Exposure

The duration of exposure to study drug in M13-538 will be summarized for the Open-Label Treated Population by the following groups:

1. Upadacitinib 6 mg BID/15 mg QD

This includes upadacitinib 6 mg BID or 15 mg QD exposure from subjects who never titrated, as well as the upadacitinib 6 mg BID or 15 mg QD exposure prior to dose titration for subjects who titrated (censored at the time of up titration to 12 mg BID/30 mg QD).

2. Upadacitinib 12 mg BID/30 mg QD

This includes upadacitinib 12 mg BID or 30 mg QD exposure for subjects who titrated up (censored at the time of down titration to 6 mg BID/15 mg QD for subjects who titrated up and back down).

3. Upadacitinib 6 mg BID/15 mg QD post down titration

This includes upadacitinib 6 mg BID/15 mg QD exposure after down titration for subjects who titrated up and back down.

4. Any upadacitinib

This includes any upadacitinib exposure in Study M13-538.

The first three exposure groups are mutually exclusive in terms of exposure, and the three groups combined is represented by the fourth group.

The duration of exposure to study drug will be summarized for each exposure group as specified above, with the number of subjects, mean, standard deviation, median, minimum and maximum values. In addition, the number and percentage of subjects exposed to study drug will be summarized for the following cumulative duration intervals.

Open-label exposure:

- ≥ 6 months
- ≥ 12 months
- ≥ 18 months
- ≥ 2 years
- ≥ 2.5 years
- ≥ 3 years
- ≥ 4 years
- ≥ 5 years

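### Adverse event rates count events up to 30 days after the last dose but divide by days on drug only, and the SAP does not say which exposure group receives post-dose events

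*SAP*

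**What the plan says.** The treatment-emergent window in SAP 10.2 opens at the first open-label dose and closes "no more than 30 days after the last dose of open-label study drug". Protocol 8.1.6.2.1 sets the same limit: "Adverse events starting more than 30 days following discontinuation of study drug will not be included in summaries of treatment-emergent AEs".

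For the rate, SAP 10.2.1 says that "the numerator of the overall rate will be the total number of TEAEs reported for" the event in question, so one subject may contribute several. It then says that "the denominator of the rates will be the total number of days exposed to study drug summed across all treated subjects", converted to years at 365.25 days, and adds: "Please refer to Section 8.1 for the calculation of study drug exposure".

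SAP 8.1 divides time on drug by dose state. Group 1 (6 mg BID/15 mg QD) is "censored at the time of up titration to 12 mg BID/30 mg QD". Group 2 (12 mg BID/30 mg QD) is cut in the same way at down-titration. Group 3 is time on the lower dose after down-titration, and group 4 is any upadacitinib. On how they relate, SAP 8.1 says: "The first three exposure groups are mutually exclusive in terms of exposure". Nothing there adds time after the last dose, and no section assigns post-dose events to a group.

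**The concern.** A rate per patient-year needs events and time taken over the same span. Here the numerator covers drug time plus a 30-day tail, and the denominator covers drug time only. Any event in the tail is counted against time that is never counted.

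The effect need not be equal across groups. A subject who changes dose brings no off-drug tail to the group being left. The tail follows the last dose, and it weighs most where exposure is short.

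Exposure-adjusted rates by exposure group are the main adverse event output (SAP 10.1) in a study whose central purpose is long-term safety (Protocol 5.6). They also drive a reporting rule: an event is tabulated as frequent if it reaches 2 events per 100 patient-years in any exposure group (SAP 10.2.2 and 10.2.4). A single short-exposure group can therefore decide what is listed.

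**Working it through.** The documents state no adverse event rate and no patient-years by group, so there is no figure to reproduce.

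**Inputs from the documents**
- 494 subjects enrolled and about 312 weeks of treatment, which is 312 × 7 = 2184 days (SAP 4.2).
- 30-day tail (SAP 10.2); 365.25 days per year and the cut-off of 2 per 100 patient-years (SAP 10.2.1 and 10.2.2).
- No return to the higher dose after a reduction (SAP 4.2), so every group 3 subject takes the last dose in group 3.

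**Assumptions, not in the documents**
- D = mean days on drug per subject in the group.
- f = share of the group's subjects whose last dose falls in that group.
- k = event rate in the tail divided by the on-drug rate.
- Post-dose events go to the group of the last dose, and every tail is followed for the full 30 days.

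**Formula**

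Reported rate = on-drug rate × (1 + f × k × 30/D), so the relative excess is f × k × 30/D.

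**Any upadacitinib (f = 1), k = 1**
- Drug time at full follow-up: 494 × 2184/365.25 = 2953.9 patient-years.
- Uncounted tail: 494 × 30/365.25 = 40.6 patient-years.
- Excess: 40.6/2953.9 = 30/2184 = 1.4%. This is the smallest value for k = 1, because early dropout shortens D.
- Mean 3 years: 30/1095.75 = 2.7%. Mean 2 years: 30/730.5 = 4.1%.

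**Group 3 (f = 1), k = 1**
- Mean 1 year: 30/365.25 = 8.2%. Mean 0.5 year: 30/182.6 = 16.4%.
- An on-drug rate of 10.0 per 100 patient-years would be reported as 10.82 or 11.64.
- At 8.2%, an on-drug rate of 2/1.082 = 1.85 reaches the cut-off.

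**Groups 1 and 2**

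Here f is below 1 wherever subjects titrate out, so 30/D alone overstates the excess. At f = 0.5 and a mean of 1 year it is 4.1%, not 8.2%.

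An illustrative split, with every count below 494 and every duration assumed: 150 subjects titrate up and 30 of them come back down. Mean exposure is 4 years if never titrated, 0.5 year before up-titration, 3.5 years on the higher dose if kept (2 years if later reduced), and 1 year after reduction.

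| Group | Drug patient-years | Tail patient-years | Excess (k = 1) |
|---|---|---|---|
| 1 | 344 × 4 + 150 × 0.5 = 1451 | 344 × 30/365.25 = 28.25 | 1.95% |
| 2 | 120 × 3.5 + 30 × 2 = 480 | 120 × 30/365.25 = 9.86 | 2.05% |
| 3 | 30 × 1 = 30 | 30 × 30/365.25 = 2.46 | 8.2% |
| Any | 1961 | 40.57 | 2.1% |

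With 200 up and 60 back down at the same durations, groups 1 and 2 are both at 1.89% and group 3 stays at 8.2%.

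One caution on the cut-off: in a group of only 30 patient-years a single event gives 100/30 = 3.3 per 100 patient-years, and still 100/32.46 = 3.1 with the tail added. The choice of denominator decides listing only when group 3 is larger than that.

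**The case against.** The strongest reply is that this is a disclosed convention. The tables are labelled as rates per patient-years of study drug exposure, and event counts and exposure years are shown beside each rate. No between-group test is planned, and any error is upward, which is the cautious direction for safety. That stands as far as it goes, but disclosing the denominator does not make it match the numerator.

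The effect is also conditional. If no events fall in the tail (k = 0), the planned rate equals the on-drug rate, and adding tail time would understate it: with f = 1 and D = 182.6 days, by 30/(182.6 + 30) = 14%. Protocol 3.0 gives an effective half-life of about 3 hours, so k below 1 is possible. So is k above 1 when subjects stop because of an adverse event. The documents settle neither. This limits how the aligned rate should be described: it is the rate over the treatment-emergent window, not over drug time alone.

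A reader might infer that the comparison of 6 mg BID/15 mg QD with 12 mg BID/30 mg QD is biased. The documents do not support that. They give neither f nor D for those groups, and in the illustrative splits the two move together at about 2%. Nor may the 8% to 16% figures be carried over to groups 1 and 2 or to the overall rate.

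Finally, assigning post-dose events to the last dose group is an assumption, not an SAP rule. If they went only to any upadacitinib, that group alone would be inflated and the events in groups 1 to 3 would no longer add up to it. The missing rule is itself part of the problem.

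**Conclusion.** The mismatch is explicit in SAP 10.2, 10.2.1 and 8.1, and no section resolves it. Its size is small overall: with k = 1 and complete 30-day follow-up, 1.4% for any upadacitinib at 312 weeks, rising to a few per cent with shorter mean exposure.

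It could be material for the post-down-titration group, where f = 1. Short exposure there is plausible, because reduction from 30 mg to 15 mg QD at the investigator's discretion came only with Amendment 5 (November 2019). Reduction for safety or tolerability was, however, allowed at any visit, and the group's actual exposure is not given.

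This is a worthwhile refinement, not a flaw that threatens the study's conclusions.

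**What to change.** In SAP 10.2.1:
- Define patient-years at risk as days on drug plus the shorter of 30 days or the time to last contact or death.
- Credit both the post-dose events and the post-dose time to the exposure group of the last dose.
- Apply this to the rates in SAP 10.2.1 to 10.2.5.
- Keep the drug-days-only rate as a secondary column.

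The data should largely exist: Protocol 6.7 collects adverse events to 30 days after discontinuation, and Protocol 5.1 and 5.4.1 plan a contact at about that time for all subjects.

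The cost is a short SAP change, a last-contact date and a second denominator to program and reconcile with SAP 8.1. Rates will fall slightly and differ from older programme tables. A footnote should state that the aligned rate describes the treatment-emergent window.
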